5.2.1.3 Handling of Treatment Arms

Analyses in the FAS and the tumor response-evaluable population will be based on the randomized treatment arm in principle.

Analyses in the AT population will be based on the actual treatment given to each subject.

5.2.2. Patient Baseline Characteristics

A list of patient baseline characteristics to be measured at entry is presented in Table 5-6.

For ECOG PS, both data obtained at randomization and data entered in “Vital Signs and ECOG (At the time of Randomization)” of the CRF will be used.

For the presence or absence of measurable lesions, both data obtained at randomization and data entered in “Tumor Imaging (Baseline)” of the CRF will be used. In the data from “Tumor Imaging (Baseline),” a measurable lesion is determined as being present when a target lesion is present, and a measurable lesion is determined as being absent when a target lesion is absent.

The number of metastatic organs is defined as the number of “sites of lesions” recorded in “Target Lesion” and “Non-target Lesion” at predose. However, “Stomach” will not be treated as a metastatic organ because all stomach lesions are primary lesions. The number of metastatic organs will be counted as one if multiple metastases are recorded in the same organ, and regional lymph nodes and distant lymph nodes are counted as the same organ. Metastatic organs recorded as “Other” will also be counted respectively in “Number of metastatic organs.”

If multiple measurements are available before treatment initiation, the most recent data before treatment initiation will be used.

Among the patient characteristic factors listed in Table 5-6, the factors used for efficacy analysis are presented in Table 5-7, and the details of categories of each factor are presented in Table 5-8.

If data are missing, the category will be indicated as “Missing.” Missing data will be excluded from the denominator used to calculate proportions and from statistical tests.

Table 5-6 Characteristic factors

Parameter	Factor
Patient baseline characteristics	Sex, age, race, country, height, weight, BSA, ECOG PS
Disease characteristics	Presence/absence of primary lesion, primary site, histological type, detail of diffuse type, detail of intestinal type, HER2, clinical stage, presence/absence of measurable lesion, sum of diameters of target lesions, category of the number of metastatic organs, metastatic organ category, presence/absence of liver metastasis, peritoneum metastasis, ascites, and lymph node metastasis, JCOG Index*
Prior treatment	Neoadjuvant chemotherapy (yes/no, regimen, detail of chemotherapy), adjuvant chemotherapy (yes/no, regimen, detail of chemotherapy), prior gastrectomy (yes/no, detail of surgery, outcome), other therapy (yes/no)
Laboratory values	Hemoglobin, white blood cell count, neutrophil count, lymphocyte count, platelet count, AST, ALT, ALP, albumin, bilirubin, creatinine, creatinine clearance, Na, K, corrected Ca, CRP, LDH, urine protein, CEA, CA19-9

*JCOG Index: Number (0 to 4) of conditions that apply to a patient among the following risk factors: ECOG PS \geq 1, number of metastatic organs \geq 2, no prior gastrectomy, and ALP deviation from the institutional upper limit of normal (ULN).¹¹⁾

Table 5-7 Factors used for analysis of each characteristic factor

Parameter	Factor
Patient baseline characteristics	Sex, age category 1, age category 2, country, BSA category, ECOG PS
Disease characteristics	Presence/absence of primary lesion, primary site, histological type, detail of diffuse type, detail of intestinal type, HER2, clinical stage, presence/absence of measurable lesion, category of the number of metastatic organs, metastatic organ category, presence/absence of liver metastasis, peritoneum metastasis, ascites, and lymph node metastasis
Prior treatment	Neoadjuvant chemotherapy (yes/no), adjuvant chemotherapy (yes/no), prior gastrectomy (yes/no), other therapy (yes/no)
Laboratory values	CEA category, CA19-9 category

Table 5-8 Details of categories

Category	Details
Sex	Male, female
Age category 1	<65 years, ≥65 years
Age category 2	<75 years, ≥75 years
Country	Japan, Korea
BSA category	<1.250, ≥1.250 to <1.500, ≥1.500
ECOG PS	0, 1
Primary site	Stomach, gastroesophageal junction
Histological type	Diffuse type, intestinal type, unknown
Detail of diffuse type	Poorly differentiated adenocarcinoma, signet-ring cell carcinoma, mucinous adenocarcinoma
Detail of intestinal type	Well-differentiated tubular adenocarcinoma, moderately differentiated tubular adenocarcinoma, papillary adenocarcinoma
HER2	Negative, positive (IHC 3+), positive (IHC 2+ / FISH+), unknown
Clinical stage	Stage IV, recurrent
Category of the number of metastatic organs	1, 2, ≥3
Metastatic organ category	Liver, lung, regional lymph nodes, distant lymph nodes, peritoneum, ascites, pleura, pleural effusion, bone, bone marrow, brain, skin, adrenal glands, esophagus, colon and rectum, ovary, pancreas, other
JCOG Index	Good risk (0 or 1), moderate risk (2 or 3), poor risk (4)
Neoadjuvant/adjuvant chemotherapy	Chemotherapy, chemoradiotherapy, radiotherapy
Detail of chemotherapy	Paclitaxel, Abraxane, docetaxel, irinotecan, S-1, capecitabine, 5-FU, UFT, oxaliplatin, cisplatin, leucovorin, trastuzumab, other
CEA category	≤ institutional ULN, > institutional ULN
CA19-9 category	≤ institutional ULN, > institutional ULN

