8.1 Inclusion Criteria

Patients must fulfill all of the following criteria at the time of randomization in this study: The rationale is provided in “26.5 Rationale for inclusion criteria”.

- (1) Histologically confirmed adenocarcinoma of the stomach or esophagogastric junction with metastatic or recurrent disease.
- (2) Measurable or evaluable metastatic lesion(s), according to RECIST version 1.1 detected by CT scan or MRI for response evaluation within 21 days prior to randomization.
- (3) Negative or unknown for HER2 testing.
- (4) No prior treatment (e.g. radiotherapy, chemotherapy, hormonal therapy) for gastric cancer.
 - Adjuvant chemotherapy is permitted if more than 180 days has elapsed between the end of adjuvant therapy and first recurrence. Adjuvant chemotherapy with platinum agent is not permitted.
- (5) ECOG PS of 0 to 1.
- (6) At least 20 years of age^{*1} at the time of informed consent.
- (7) The following bone marrow, liver, and kidney function parameters measured within 14 days prior to randomization:
 - 1) Neutrophil count $\geq 1500/\text{mm}^3$ ^{*2}
 - 2) Hemoglobin ≥ 8.0 g/dL^{*2}
 - 3) Platelet count $\geq 100000/\text{mm}^3$ ^{*2}
 - 4) Total bilirubin ≤ 1.5 mg/dL
 - 5) AST, ALT levels ≤ 3 x ULN, or ≤ 5 x ULN in the presence of liver metastasis
 - 6) ALP levels ≤ 2.5 x ULN, or ≤ 5 x ULN in the presence of liver metastasis
 - 7) Creatinine clearance ≥ 60 mL/min^{*3}
- (8) Life expectancy of at least 90 days after randomization.
- (9) Capable of oral intake.
- (10) Written informed consent to participate as a subject in this clinical study.

^{1*} : For 75 years of age or older patient, pay careful attention to manage adverse events.

^{2*} : If patients received blood transfusion or treatment with any blood product or hematopoietic factor such as G-CSF, it must be confirmed the data is obtained more than 14 days after the last blood transfusion or treatment.

^{3*} : A value obtained from a urine collection, if available. Otherwise an estimate by the Cockcroft-Gault formula:

Estimated creatinine clearance (mL/min)
= $(140 - \text{age}) \times \text{Body weight (kg)} / [72 \times \text{Serum creatinine (mg/dL)}]$
For women, the obtained value is multiplied by a factor of 0.85.

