14.1.1.2 Tumor Definitions

(1) Measurable Lesions

Measurable tumor lesions: Lesions that can be accurately measured in at least 1 dimension with the longest diameter (to be recorded) ≥ 10 mm by CT or MRI scan if using slice thickness of 5 mm or less, or at least double the slice thickness of CT or MRI scan if the slice thickness is >5 mm.

Measurable malignant lymph nodes: A lymph node must be considered pathologically enlarged with high suspicion of metastasis and measure ≥ 15 mm in the short axis when assessed by CT or MRI scan. The short axis is defined as the longest linear dimension perpendicular to the node's longest diameter as assessed within the same plane that the scan was acquired.

Only measurable lesions can be selected as target lesions.

(2) Non-measurable Lesions

Non-measurable lesions include:

- Small metastatic tumor lesions that have a longest dimension less than 10 mm or if slice thickness is greater than 5 mm less than twice the slice thickness.
- Abnormal and suspected metastatic lymph nodes that are ≥ 10 mm to <15 mm in the short axis.
- Truly non-measurable lesions (e.g., ascites).
- Primary lesion (in case primary lesion is not able to be evaluated as non-measurable lesion, evaluation of the lesion will not be performed.)

All non-measurable lesions can only be selected as non-target lesions.

(3) Target Lesions

- All measurable lesions up to a maximum of 2 lesions/organ and 5 lesions in total, representative of all involved organs should be identified as target lesions.
- Target lesions should be selected on the basis of their size (visceral lesion with the longest diameter and lymph node with the measurement of short axis), be representative of all involved organs, but in addition should be those that lend themselves to reproducible repeated measurements.
- When recording tumor measurements the longest diameter will be measured for

tumor lesions. For pathological lymph nodes, the short axis will be measured.

- Lymph nodes identified as target lesions should always have the actual short axis measurement recorded, even if the nodes regress to below 10mm on study. This means that when lymph nodes are included as target lesions, the sum of lesions may not be zero even if complete response (CR) criteria are met.
- The sum of the diameters for all target lesions at baseline will be calculated as the baseline sum. The baseline sum will be used as a reference for follow-up tumor assessment.

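### The metastatic-organ count drops the primary lesion only when its site is recorded as stomach, so a gastroesophageal-junction primary recorded under another site name is counted as a metastatic organ

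*SAP*

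**What the plan says.** **The count.** SAP 5.2.2 begins "The number of metastatic organs is defined as the number of" lesion sites recorded under the target and non-target headings before dosing. A site recorded as *Stomach* "will not be treated as a metastatic organ because all stomach lesions are primary lesions". Two grouping rules follow. Several deposits within a single organ count once. For nodes, "regional lymph nodes and distant lymph nodes are counted as the same organ". Metastatic organs entered as *Other* are counted as well.

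**Who is enrolled.** Protocol 8.1 admits "Histologically confirmed adenocarcinoma of the stomach or esophagogastric junction with metastatic or recurrent disease". SAP Table 5-8 gives primary site two values: "Stomach, gastroesophageal junction".

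**Where the primary is recorded.** Protocol 14.1.1.2 includes in its list of non-measurable lesions "Primary lesion (in case primary lesion is not able to be evaluated as non-measurable lesion", with the proviso that such a primary is then not evaluated. Non-measurable lesions can be chosen only as non-target lesions, and non-target sites feed the count.

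**Organ categories.** The metastatic organ category in Table 5-8 includes "peritoneum, ascites, pleura, pleural effusion, bone, bone marrow, brain, skin, adrenal glands, esophagus" among its levels. It has no level for the junction.

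**Where the count is used.** Its category (1, 2, ≥3) and the metastatic organ category are both in SAP Table 5-7. Section 6.3 applies the Table 5-7 factors to the OS subgroup hazard ratios, forest plot and interaction p-values. Sections 7.1.1.2 and 7.1.1.3 apply them to ORR and DCR, and 7.1.2 and 7.1.3 carry the OS analyses over to PFS and TTF. A count of 2 or more is also one of the four JCOG Index conditions under Table 5-6.

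**The concern.** The exclusion has a stated purpose: the primary tumor is not a metastasis. It is implemented through a site name that covers only one of the two eligible primary sites. That every stomach lesion is a primary does not make every primary a stomach lesion.

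Protocol Appendix 1 makes the gap practical. It defines the junction area as reaching 2 cm above the junction, so *esophagus* is a natural label for some junction primaries. SAP 5.2.2 would treat that label as a metastatic organ.

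Three outputs are at stake:

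- **Organ-number subgroup.** Some junction patients sit one level too high, which mixes the strata of a prognostic factor.
- **Metastatic organ category.** The primary itself can appear as an esophageal metastasis.
- **JCOG Index.** Some patients gain a risk point that comes from their primary tumor.

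**Working it through.** The plan states no figure for this rule, so there is none to reproduce. The check applies the rule literally to example records and compares it with the same rule after the primary is removed whatever its label.

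**Rules compared**

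- *Literal* = number of distinct recorded sites, less *Stomach*, with regional and distant nodes merged.
- *Primary removed* = literal count, less one if the junction primary stands under another site name that holds no true metastasis.

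| Recorded sites | Literal count (category) | Primary removed (category) |
|---|---|---|
| Stomach primary, liver | 1 (1) | 1 (1) |
| Junction primary as esophagus, liver | 2 (2) | 2 − 1 = 1 (1) |
| Junction primary as esophagus, liver, distant nodes | 3 (≥3) | 3 − 1 = 2 (2) |
| Junction primary as esophagus, liver, distant nodes, peritoneum | 4 (≥3) | 4 − 1 = 3 (≥3) |

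The first two rows describe the same metastatic burden, one liver site. They differ only in where the primary lies and how it was labeled, yet they fall in different subgroup levels. The last row shows that a patient whose correct count is already 3 or more does not change level.

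**JCOG Index**

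The index is the number of conditions met among PS ≥1, at least 2 metastatic organs, no prior gastrectomy, and ALP above the institutional limit. Let *o* be the number met among the three conditions other than organ count. When the literal rule lifts the count from 1 to 2, the index goes from *o* to *o* + 1:

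| *o* | Index | Risk group |
|---|---|---|
| 0 | 0 → 1 | good → good |
| 1 | 1 → 2 | good → moderate |
| 2 | 2 → 3 | moderate → moderate |
| 3 | 3 → 4 | moderate → poor |

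Example: PS 0, no prior gastrectomy, normal ALP, junction primary labeled esophagus, liver metastasis. Here *o* = 1 and the true count is 1, so the index should be 1 (good risk). The literal rule gives 2 (moderate risk). A move from 2 to 3 organs adds no index point, because the condition is already met.

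**How many patients**

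The documents give no frequencies. The share overcounted is *j* × *r*, where *j* is the share of patients with a junction primary and *r* is the share of those whose primary is recorded as a lesion under a name other than stomach. Purely as assumptions, take *j* = 5% to 10% and *r* = 30% to 80%:

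- low: 0.05 × 0.30 = 0.015, and 0.015 × 650 ≈ 10 patients of the planned FAS;
- high: 0.10 × 0.80 = 0.08, and 0.08 × 650 = 52 patients.

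If every junction primary was entered as stomach, *r* = 0 and no patient is affected. These are patients overcounted by one. Fewer change subgroup level, as the last row of the first table shows.

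**The case against.** **The CRF site list is not in the documents.** The list in Table 5-8 is an analysis category, not the CRF list. It has no stomach level either, yet 5.2.2 names stomach as a recorded site. Sites may have entered all junction primaries as stomach, and then nothing happens. This stands, and it is why the size is unknown. It does not make the rule correct, since the result then depends on a coding habit that the SAP does not state.

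**Not every primary enters the data.** A primary that cannot be evaluated as a non-measurable lesion is not evaluated at all. In addition, the sentence on *Other* speaks of metastatic organs, so a primary entered there could fairly be left out. Both points narrow the problem. Entry as *esophagus* remains unaddressed.

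**The consequences are limited.** The interaction p-values serve to check uniformity among strata and carry no alpha. Liver, peritoneal, ascites and lymph-node involvement have their own subgroups. This stands too.

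**Stronger readings that a reader might infer**

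- *That counting ascites beside peritoneum, or pleural effusion beside pleura, is the same error.* The documents do not support this. The SAP lists these as separate items: ascites and peritoneal metastasis are separate factors in Tables 5-6 and 5-7, and all four are separate levels in Table 5-8. Only the lymph-node sites are merged. Nothing says the true count is 1, and the documents do not show how the source of the JCOG Index counted effusions. It is a counting convention, on which either choice is defensible.
- *That the JCOG Index distorts the OS subgroups.* The index is in Table 5-6 but not in Table 5-7. It enters the baseline tables and a Wilcoxon comparison of the arms.

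**Conclusion.** The point holds as a narrow gap in a derivation rule. The exclusion in 5.2.2 does not achieve its stated purpose for junction primaries recorded under a name other than stomach. Each such record overstates the number of metastatic organs by one, unless a true metastasis shares that name. The subgroup level changes only when the count crosses 1 to 2 or 2 to 3. The JCOG risk group changes only on a move from 1 to 2 with exactly one or three of the other conditions met.

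The conclusion rests on the text of 5.2.2 read literally and on at least some junction primaries being entered as *esophagus* or a similar site. The second cannot be verified from the documents, and the range of about 10 to 52 patients is only as good as its assumed inputs.

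It would be wrong to infer a bias in the primary result. The stratified log-rank test uses PS, measurable lesion and country, none of which depends on this count. The rule uses pre-treatment data and is the same in both arms. What is affected is the labeling of strata in supporting analyses and the description of baseline prognosis. This is a minor point, worth correcting because the correction is nearly free.

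**What to change.** In SAP 5.2.2, state that any lesion identified as the primary, whether in the stomach or at the gastroesophageal junction, is left out of both the metastatic-organ count and the metastatic organ category, whatever site label it carries. Identify it from two variables already listed in Table 5-6: primary site and presence or absence of the primary lesion. Derive the organ-number category and the JCOG Index from the resulting count.

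The cost is one sentence, a small change to the derivation program, and a check of the site entries for junction primaries before database lock. That check is needed to separate a junction primary labeled *esophagus* from a true esophageal metastasis. If version 1 of the SAP is already final, Section 8 provides for a revised version with the background and reason recorded.

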5.2.3. Statistical Methods

5.2.3.1 Summary Statistics for Continuous Data

Summary statistics for continuous data, if indicated, include the sample size, minimum, maximum, median, first quartile, third quartile, mean, and standard deviation.

5.2.3.2 Proportion

Proportions will be calculated using the following formula:

$$\text{Proportion (\%)} = \frac{\text{Number of relevant subjects}}{\text{Number of subjects in each arm in the analysis population}} \times 100$$

5.2.3.3 Test Methods

(1) Patient baseline characteristics

The test methods used to investigate whether patient baseline characteristics are biased between the treatment arms are presented in Table 5-9.

Table 5-9 Test methods for patient baseline characteristics

Test method	Parameter	Factor
t test (homogeneity of variance)	Patient baseline characteristics	Age, height, weight, BSA
	Disease characteristics	Sum of diameters of target lesions
	Laboratory values	Hemoglobin, white blood cell count, neutrophil count, lymphocyte count, neutrophil/lymphocyte count ratio, platelet count, AST, ALT, ALP, albumin, bilirubin, creatinine, creatinine clearance, Na, K, corrected Ca, CRP, LDH, urine protein, CEA, CA19-9
Fisher's exact test	Patient baseline characteristics	Sex, age category 1, age category 2, country, ECOG PS
	Disease characteristics	Presence/absence of primary lesion, primary site, clinical stage, presence/absence of measurable lesion, presence/absence of liver metastasis, peritoneal metastasis, ascites, and lymph node metastasis
	Prior treatment	Presence/absence of neoadjuvant chemotherapy, presence/absence of adjuvant chemotherapy, prior gastrectomy, other therapy
	Laboratory values	CEA category, CA19-9 category
χ^2 test (Pearson chi-squared test without continuity correction)	Patient baseline characteristics	–
	Disease characteristics	Histological type, HER2
	Prior treatment	–
Wilcoxon test (normal approximation with continuity correction)	Patient baseline characteristics	BSA category
	Disease characteristics	Category of the number of metastatic organs, JCOG Index
	Laboratory values	Urine protein To be tested after it is converted into numbers as follows: –1: – 0: +- 1: + 2: 2+ 3: 3+ 4: 4+

(2) Survival analysis

A stratified log-rank test or log-rank test will be used to compare the distribution of survival times between the treatment arms. The endpoints of OS, PFS, and TTF will be evaluated.

(3) Comparison of proportions

Fisher's exact test will be used to compare the proportion of subjects between the treatment arms. The endpoints of ORR and DCR will be evaluated. For the endpoints of ORR and DCR, a Cochran–Mantel–Haenszel test stratified by the allocation adjustment factors will also be conducted.

5.2.3.4 Model Analysis

(1) Cox proportional hazards model

A Cox proportional hazards model will be used to estimate the hazard ratio. The hazard function at time t is defined as follows:

$$\lambda(t; \mathbf{X}) = \lambda_0(t) \exp(\mathbf{X}\boldsymbol{\beta}),$$

where $\lambda_0(t)$ is a baseline hazard function, \mathbf{X} is a covariate, and $\boldsymbol{\beta}$ is a regression coefficient.

5.2.3.5 Estimation Methods

(1) Confidence interval of proportions

The confidence interval of ORR, DCR, and the proportion of subjects with adverse events will be calculated using the F distribution-based method proposed by Clopper and Pearson (1934).⁸⁾

The upper limit of confidence interval P_U and the lower limit of confidence interval P_L will be estimated using the following formulas, where P is a proportion, X is the number of subjects with events, N is the number of subjects in the analysis population, and α is a two-sided significance level:

$$P = X/N$$

$$P_U = \frac{v_1 F_{v_1, v_2}(\alpha/2)}{v_2 + v_1 F_{v_1, v_2}(\alpha/2)}, v_1 = 2(X + 1), v_2 = 2(N - X)$$

$$P_L = \frac{v_2}{v_2 + v_1 F_{v_1, v_2}(\alpha/2)}, v_1 = 2(N - X + 1), v_2 = 2X$$

(2) Estimation of survival curves

The survival time function $S(t_j)$ will be estimated using the following formula based on the Kaplan–Meier method, where $t_1 < t_2 < \dots < t_N$ is the time of event onset in subject $j = 1, \dots, N$, n_j is the number of subjects at risk at time t_j , and d_j is the number of subjects with events:

$$\hat{S}(t_N) = \prod_{j=1}^N \left(1 - \frac{d_j}{n_j}\right)$$

(3) Confidence interval of MST

The confidence interval of MST will be calculated using the method based on the sign test for censored data.⁹⁾

The standard error of survival time function $S(t_j)$ will be estimated using the following formula:

$$\hat{\sigma}(\hat{S}(t_N)) = \hat{S}(t_N) \sqrt{\sum_{j=1}^N \frac{d_j}{n_j(n_j - d_j)}}$$

The confidence interval of MST is defined as the time of event onset within the following interval, where α is a two-sided significance level:

$$\left\{t: (1 - \hat{S}(t) - 0.5)^2 \leq \chi_1^2(\alpha) \hat{\sigma}^2(\hat{S}(t))\right\}$$

(4) Confidence interval of hazard ratios

The covariance matrix of a regression coefficient estimate $\hat{\boldsymbol{\beta}}$ is expressed using the following formula, where $l(\boldsymbol{\beta})$ is a log-likelihood function:

$$\hat{\mathbf{V}}(\hat{\boldsymbol{\beta}}) = - \left[\frac{\partial^2 l(\hat{\boldsymbol{\beta}})}{\partial \boldsymbol{\beta} \partial \boldsymbol{\beta}'} \right]^{-1}$$

Ties in survival time, if any, will be processed using the Breslow method.

The confidence interval of a hazard ratio estimate of the p th covariate, $\exp(\hat{\beta}_p)$, will be estimated using the following expression,¹⁰⁾ where α is a two-sided significance level and $\hat{V}_p(\hat{\boldsymbol{\beta}})$ is the p th diagonal element in the covariance matrix $\hat{\mathbf{V}}(\hat{\boldsymbol{\beta}})$:

$$\exp\left(\hat{\beta}_p \pm Z_{\alpha/2} \sqrt{\hat{V}_p(\hat{\beta})}\right)$$

